#### 13. Conduct of the trial

After eligibility is confirmed and informed consent is obtained, the following assessments will occur. See 'Schedule of Events' in the appendix.

#### 13.1 Screening (-90 days to 0 days before the index surgical event)

- Written informed consent
- Eligibility criteria including EuroSCORE I and pregnancy test (dipstick or beta HCG) for women of childbearing potential

# 13.2 Preoperative/baseline assessments (-30 days to 0 days before the index surgical event)

- Recheck eligibility if >30 days since initial screening
- EuroSCORE I
- EQ-5D-3L
- Standard 12-lead Electrocardiogram (ECG)
- Demographics
- Medical/Cardiac History
- Height and Weight measurements
- Concomitant Medications
- Preoperative laboratory values (preoperative value closest to the index surgical date, no more than 30 days prior to the surgery date)

 Randomisation through the eCRF; whenever feasible, randomisation will occur no more than 24 hours prior to the scheduled surgery to minimise the risk of losing randomised patients due to unplanned surgery cancellations

#### 13.3 Index Cardiac Surgery (Day 0)

- Surgical/procedure details
- Perioperative medications (anti-fibrinolytics, vasoactive medications) and intravenous (IV) fluids
- Reporting of all protocol-defined "trigger events" (see section 11.5) and transfusions
- Clinical events (see section 14.12)
- Intraoperative laboratory values

# 13.4 Postoperative period (Day of surgery until hospital discharge or postoperative day 28, whichever comes first)

- Reporting of all protocol-defined "trigger events" (see section 11.5) and transfusions
- Clinical events (see section 14.12.1)
- EQ-5D-3L
- Standard 12-lead ECGs will be performed on the day after surgery and on day 4-6 postoperatively or at hospital discharge, whichever comes first
- Postoperative laboratory values

#### 13.5 3 month Follow-up

- EQ-5D-3L
- Health Economics questionnaire

#### 13.6 6 month Follow-up

- Clinical events (see section 14.12.2)
- Emergency room (ER) visits and hospital admissions since discharge from the index hospitalisation
- EQ-5D-3L
- Obtain the last available standard 12-lead ECG done for clinical purposes
- Concomitant Medications

# 14. Clinical procedures and safety evaluations

#### 14.1 Informed Consent

Once deemed an appropriate candidate for the trial, the patient will be informed of the possibility of trial participation. Eligible patients will be provided with a written version of the participant information sheet (PIS). The benefits and risks of participating in the trial will be explained to the patient, and the patient will be provided an opportunity to read the PIS and ask any questions he/she may have. Prior to conducting any trial-related procedures, the patient must provide consent to participate by signing\* the Research Ethics Committee (REC) approved consent form.

The participant will be given sufficient time to consider the information, and afforded the opportunity to ask questions of the Investigator, their GP or other independent parties to decide whether they will participate in the trial. There will be no requirement that a patient must have the

PIS for a minimum duration prior to consent considering the often emergency/urgent requirements in cardiac surgery. This will apply in urgent cases only and not elective/planned surgery. However, every effort should be made to maximise the amount of time the patient has for consideration of trial enrolment, ensuring they feel that their questions have been addressed and they are happy to take part. Patients and carers may attend once or more times, or have subsequent telephone or video calls, to carefully consider their participation.

Informed consent will be taken by the Principal Investigator (PI) at site or an appropriately qualified individual to whom this task has been delegated, prior to undertaking any trial-related procedures. This will include research nurses and practitioners if compatible with local policy. All participants will be asked for consent to access to their medical records.

Where appropriate and as per local NHS Trust policy guidelines, consent will be obtained either over the telephone or by video call between the participant and the clinician/researcher. The Video/Telephone Consent Form will be completed by the researcher or delegated site person performing consent, confirming that the participant has understood the information and consent process. A copy of the Video/Telephone Consent Form will be given to the participant at the next available opportunity or sent via post, if local trust policy allows, and a copy will be filed in the participants medical records.

\*This includes consent obtained by telephone or video call.

#### 14.2 Demography

This includes date of birth, sex and ethnicity.

#### 14.3 Medical/Cardiac History

Data will be collected from patients at baseline consisting of demographics, previous cardiac investigations, and previous cardiac and non-cardiac history.

#### 14.4 Pregnancy test

A negative pregnancy test (dipstick or beta HCG) is required to be obtained prior to randomisation for women of childbearing potential.

#### 14.5 Standard 12-lead ECG

A 12-lead ECG will be performed preoperatively, on the day after surgery and on day 4-6 postoperatively or at hospital discharge (whichever comes first). We will also collect the last ECG performed for clinical purposes up to the 6 month follow-up visit.

#### 14.6 Body weight and height

Body weight and height will be recorded at baseline.

#### 14.7 EuroSCORE I

The preoperative EuroSCORE I will be collected in the eCRF.

#### 14.8 Surgical details

Details about the type of surgical procedure, interventions, duration and complications will be recorded including type of cardioplegia, blood loss, use of hemofiltration, duration of

Page 30 of 55

IRAS ID: 325425

cardiopulmonary bypass and aortic cross-clamp, presence of arrhythmias, and the use of intraaortic balloon pump/ventricular assist device. In addition, the type and volume of IV fluids administered in the first 24 hours after induction of anaesthesia will be collected in the eCRF.

#### 14.9 Medications

Anti-fibrinolytic agents, vasoactive medications and type and volume of IV fluid administered will be recorded in the eCRF for the intraoperative and postoperative periods.

#### 14.10 Laboratory tests

The following laboratory values are standard of care at most clinical institutions, and the laboratory data will be captured in the eCRF as follows:

#### 14.10.1 Preoperative laboratory values

Hb, hematocrit (HCT), platelets, red cell distribution width, INR, activated partial thromboplastin time (aPTT), fibrinogen, creatinine, and creatine kinase—MB (CKMB) or troponin (preferred)

#### 14.10.2 Intraoperative laboratory values

Lowest Hb (pre/during CPB and chest closure), lowest HCT (pre/during CPB and chest closure), lowest arterial and mixed venous pO2 (pre/during CPB and chest closure), lowest arterial and mixed venous O2 saturation (pre/during CPB and chest closure), lowest cardiac index (pre-CPB and chest closure) if measured, minimum pump flow (during-CPB)

#### 14.10.3 Postoperative laboratory values

- Hb is required to be assessed on postoperative days 1, 2, 5 ±2, and 11 ±3 while in hospital. Hb measurements that are done for clinical purposes will be collected, if more than one Hb is measured on a particular day, the lowest value for that day will be recorded in the eCRF. Any patient who is transfused, is required to have a pre- and posttransfusion Hb measurement.
- CK-MB or troponin (preferred) is required to be assessed on the first postoperative day, approximately 24 hours after the end of surgery.
- Creatinine is required to be measured on postoperative days 1, 2, 3 and 5, and otherwise as clinically indicated.
- Other laboratory values will be performed as clinically indicated or as per local guidelines and collected in the eCRF up to hospital discharge/postoperative day 28: HCT, platelets (within 2 hours of chest closure), INR, aPTT and fibrinogen (within 2 hours of chest closure), CK-MB or troponin (preferred), arterial and mixed venous O2 saturation, arterial and mixed venous pO2.

#### 14.11 Transfusions and "Trigger Events"

All protocol defined "trigger events" (per section 6.4) and all RBC transfusions will be recorded in the eCRF from the start of the index surgical procedure until hospital discharge, as well as the preand post-event/transfusion Hb times and values.

All non-RBC transfusions administered during the index hospitalisation period will be reported in the eCRF.

#### 14.12 Clinical Events

14.12.1 Clinical events from the start of surgery until hospital discharge or postoperative day 28, whichever comes first

The following clinical events will be assessed through review of the patient medical records/chart, and reported in the eCRF from the start of the index cardiac surgery until discharge or postoperative day 28, whichever comes first. All definitions are standard definitions.

- All-cause mortality
- Myocardial infarction which will be defined in accordance with the 4th Universal Definition of Myocardial Infarction
  - a) Early perioperative MI (intraoperatively or within 48 hours after surgery): Detection of cardiac troponin (preferred) or CK-MB values more than 10 times the 99th percentile of the upper limit from a normal baseline\* (i.e. the 99th percentile or less of the upper limit of normal) during the first 48 hours following surgery, and at least one of the following:
    - development of new pathological Q waves on the ECG
    - imaging evidence of new loss of viable myocardium or new regional wall motion abnormality
    - identification of a coronary dissection, new intracoronary thrombus of the new graft or native coronary artery(ies) by angiography or autopsy
    - Although a new left bundle branch block is not part of the 4th Universal Definition, we will
      include the collection of left bundle branch block to permit comparison to data collected
      in TRICS III that complied with the 3rd Universal Definition, which included left bundle
      branch block

\*or, if preoperative cardiac enzymes are elevated, the postoperative enzymes are increased by more than 10 times the upper limit of normal (ULN) from the baseline value (i.e. greater than baseline plus 10 x the ULN).

- b) Late perioperative MI (more than 48 hours after surgery): Detection of a rise and/or fall of cardiac troponin (preferred) or CK-MB values, with at least one value above the upper limit of normal, and with at least one of the following:
  - symptoms of ischemia, as long as the symptoms/signs are not explained by another proven clinical condition (pulmonary embolism, myocarditis, etc.)
  - new, or presumed new, significant ST-T wave changes or new left bundle branch block
  - development of new Q waves on the ECG
  - imaging evidence of new loss of viable myocardium or new regional wall motion abnormality
  - identification of a new intracoronary thrombus of the new graft or native coronary artery(ies) by angiography or autopsy

Percutaneous coronary intervention (PCI) related MI is included in the late MI group, and is arbitrarily defined by elevation of troponin values more than 5 times the 99th percentile of the upper limit from a normal baseline, or a rise of troponin values more than 20% if the baseline values are elevated and are stable or falling. In addition, either (i) symptoms suggestive of myocardial ischemia, or (ii) new ischemic ECG changes, or (iii) angiographic findings consistent with a procedural complication or (iv) imaging demonstration of new loss of viable myocardium or new regional wall motion abnormality are required.

New onset renal failure requiring dialysis (excluding dialysis during CPB)

Page **32** of **55** 

IRAS ID: 325425

- New focal neurological deficit (stroke) lasting more than 24 hours confirmed by clinical assessment and brain imaging
- Infection: infection will be defined as septic shock with positive blood cultures; pneumonia defined as autopsy diagnosis or roentgenographic infiltrate and at least two of the following three criteria: fever, leukocytosis, and positive sputum culture; and/or deep sternal or leg wound infection requiring intravenous antibiotics and/or surgical debridement44
- Acute kidney injury: defined by the Kidney Disease Improving Global Outcomes (KDIGO) clinical practice guideline46 a 50% increase in serum creatinine within 1 week or a 26.5 μmol/L increase within 48 hours
- Delirium: based on one of the following criteria: CAM/CAM-ICU (even on 1 occasion), or ICDSC
   > 3, or 3D-CAM, or 4AT ≥4, or more than one dose of haloperidol or similar antipsychotic drug, or documented delirium by neurologist or neurosurgeon or psychiatrist consultation
- **Gut infarction:** confirmed by imaging (e.g. angiography), autopsy, or through surgical means
- **Seizures:** defined as generalised or focal tonic-clonic movements consistent with seizure; or EEG demonstrating epileptiform discharges; or diagnosis of seizures by neurologist or neurosurgeon consultation
- **Encephalopathy:** defined as unexpected delayed awakening or severely altered mental status (unconscious despite no sedative medication for more than 5 days), or encephalopathy documented by neurologist or neurosurgeon or psychiatrist consultation

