This trial will bring together the TRICS III research team in Canada with the TITRe2 team in the UK. Both of these trials were published in the New England Journal of Medicine and are widely cited in treatment guidelines. The TRICS IV trial aims to recruit 1760 participants from 72 units in 18 countries and is of sufficient size to definitively answer the research question. Inclusion of a large UK cohort will build on the experiences of the TITRE 2 and TRICS III researchers to increase generalisability of the trial results to NHS patients.

If the trial demonstrates that a liberal strategy is superior, the risks and costs of organ injury related to untreated severe anaemia will be reduced. If the liberal strategy is not superior, the risks and costs attributable to unnecessary transfusions will be reduced. The trial will thus provide high-quality generalisable data to guide transfusion practice worldwide, regardless of its eventual results.

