#### 7.4 What are the Adverse Events Associated with Transfusion?

There are a number of complications related to transfusion that are associated with considerable morbidity and mortality. Non-infectious risks from transfusion such as transfusion related acute lung injury (TRALI), which tends to occur more frequently in patients having cardiac surgery, perhaps because of increased systematic and pulmonary inflammation with cardiac surgery, has a high case fatality rate, 5 to 13%. Additionally, administrative errors resulting in hemolytic transfusion reactions can be life-threatening. Pulmonary edema, due to the volume of RBCs occurs more frequently in patients with critical illness and cardiovascular disease transfused at a Hb of 100 g/L compared to a Hb of 70 g/L8. Although the risk of acquiring transfusion transmitted viruses is low, new emerging pathogens constantly threaten the blood supply. Unnecessary transfusions also have an impact on the care of patients. Optimum utilisation of blood components is essential as there is a continuous strain on blood systems because of increased blood utilisation. Additionally, increased transfusion results in increased resource utilisation and the cost of blood is increasing40. In an era where there are new emerging pathogens and blood shortages, it is essential for patients to be transfused appropriately.

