#### 14.12.2 Clinical events at 6 month follow-up visit

At 6 months, an in-person follow-up visit (or telephone, if in-person is not possible) will occur to capture any new hospitalisations or emergency department visits, as well as the following clinical outcomes. A telephone script has been created to facilitate collection of this data, in case an in-person visit is not possible.

- All-cause mortality
- M
- New onset renal failure requiring dialysis
- Stroke
- Surgical or non-surgical coronary revascularisation
- COVID-19 test result (if done for clinical purposes)

The following will also be collected in the eCRF at the 6 month follow-up visit:

- Details for any **ECG(s) done for any incidence of MI** that occurs up to the 6 month visit, if applicable. Sites will be requested to send de-identified copy(ies) of the ECG(s) to the DCC.
- Details for the last ECG performed for clinical purposes. Sites will be requested to send a
  deidentified copy of the ECG for adjudication to the DCC via [contact].
- A **list of all medications** that the patient is taking at the 6 month follow-up visit.

Routinely collected healthcare data via Office for National Statistics (ONS) will be used to ascertain mortality at 6 months in UK participants. A telephone contact to participants who have not died (identified from NHS SPINE data) will occur at 6 months postoperatively to assess clinical outcomes. Laboratory parameters will be determined preoperatively, intraoperatively, daily for the first three days postoperatively then every second day until day 11 and thereafter as clinically indicated while in hospital, as in TRICS III.

Page **33** of **55** 

IRAS ID: 325425

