#### 17.5 Data and Safety Monitoring Board

An independent Data and Safety Monitoring Board (DSMB) will be assembled to ensure patient safety, receive and review interim analyses, provide feedback to the SC, and ensure the trial follows the highest ethical standards. The DSMB will be provided data on safety regularly throughout the trial period, in accordance with the DSMB Charter. The safety data will include all clinical events. We will only conduct additional safety reviews if otherwise directed by the DSMB.

The DSMB will consider clinical and statistical significance, consistency of data over time, consistency of the direction of risk and benefit-risk ratios if there is consideration for recommendation for early trial discontinuation. The DSMB will have the ability to request additional safety analyses or additional interim analyses, and to convene a full committee meeting and make any further recommendations to the steering committee about the safe conduct of the trial after considering all the available data and any new external data from relevant studies. The DSMB will have access to the randomisation codes, if needed. The DSMB will reside in Canada.

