### 18.1 Assessment and management of risk

#### 18.1.1 Potential risks and hazards communicated to eligible patients

Similar to TRICS III, patients allocated to the liberal strategy may receive a transfusion that they otherwise may not have been given and which may result in a reaction. The other potential harm is that patients may not receive a transfusion when it may otherwise have been administered if they are allocated to the restrictive strategy. These patients may experience an adverse event secondary to anaemia or tissue hypoxia. The transfusion levels selected for this trial, however, are levels that we have used in TRICS III and TITRE2. They were acceptable to the centres participating in TRICS and TITRE 2 as supported by the high adherence (90.9%) to transfusion strategies. The potential harms of either transfusion strategy can still occur outside this trial since with routine care, these transfusion thresholds are commonly used. The Data Safety Monitoring Board (DSMB) will review safety reports biannually and data from the interim analysis. The DSMB will have the ability to request additional safety analyses and make recommendations about the conduct of the trial.

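### The transfusion harms that the protocol names need not be recorded as such, so the required data cannot give a count of them by arm

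*Protocol*

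**What the plan says.** Section 7.4 of the protocol sets out the harms of transfusion. It describes TRALI as a complication "which tends to occur more frequently in patients having cardiac surgery", with a case fatality of 5 to 13%. It warns that "administrative errors resulting in hemolytic transfusion reactions can be life-threatening". It adds: "Pulmonary edema, due to the volume of RBCs occurs more frequently in patients with critical illness and cardiovascular disease", the comparison there being a trigger of 100 g/L against 70 g/L. Section 18.1.1 carries this into the risks told to patients: "patients allocated to the liberal strategy may receive a transfusion that they otherwise may not have been given and which may result in a reaction".

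Section 14.12.1 fixes the reporting duty for the index stay: "The following clinical events will be assessed through review of the patient medical records/chart, and reported in the eCRF". The list that follows is death, myocardial infarction, dialysis, stroke, infection, acute kidney injury, delirium, gut infarction, seizures and encephalopathy. Section 14.12.2 has a 6-month contact "to capture any new hospitalisations or emergency department visits, as well as the following clinical outcomes"; those outcomes are death, myocardial infarction, dialysis, stroke, coronary revascularisation and a COVID-19 test result.

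Section 17.5 says of the DSMB: "The safety data will include all clinical events". It asks the board to consider benefit-risk ratios if early discontinuation is in question. The scientific abstract (Section 5) counts safety among the secondary outcomes.

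**The concern.** More red-cell transfusion is the intervention under test, and the protocol says what that intervention can do to patients. One would expect those harms to be among the events sites must report. They are not, whereas organ injuries of the kind attributed to anaemia (heart, brain, kidney, gut) are defined and collected in detail.

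The benefit-risk judgement is what suffers. If the liberal strategy wins, clinicians would adopt it without a count of reactions, TRALI or overload from the trial that supports it. If it does not win, Section 7.1 says: "If the liberal strategy is not superior, the risks and costs attributable to unnecessary transfusions will be reduced". The trial would then have no direct tally of those acute risks to set beside that statement. The choice of what sites record belongs in the protocol; an analysis plan cannot recover a variable that was never collected.

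**Working it through.** No figure in the protocol needs reproducing here. The check compares the four named harms with every place where the protocol says what is collected.

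| Protocol section | What it collects | Any of the four harms named? |
|---|---|---|
| 14.11 Transfusions and trigger events | Trigger events, RBC transfusions, haemoglobin times and values before and after; non-RBC transfusions | No |
| 14.12.1 Events to discharge or day 28 | The ten events listed above; no entry for other events | No |
| 14.12.2 Events at 6 months | Six items, plus hospitalisations, emergency visits, ECGs and medications | No |
| 8.2 and 15.2 Secondary objectives and endpoints | The clinical events, plus low output state, ventilation time, length of stay, blood products used and hospital visits | No |
| 19.5 Costs and outcomes | Much the same outcomes, plus resource use and quality of life | No |
| 24.1 Schedule of events | Refers back to the clinical events and transfusion details | No |

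**Is there another reporting route?** The protocol has no separate section for adverse events or serious adverse events. Item 16 of Section 19.5 says that clinical events are what the UK arm would usually call adverse events. The clinical event list is therefore the adverse event system as far as this document goes.

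**Can the DSMB fill the gap?** Section 17.5 lets it request additional safety analyses and make recommendations on conduct. An additional analysis works only on recorded data. The board could recommend new data collection, but the protocol does not provide for it in advance.

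**What would surface indirectly?** A severe case could contribute to death (Section 10.7 requires the cause), ventilation time, ICU stay, acute kidney injury, low output state, the surgical complications in Section 14.8, or a readmission or emergency visit. None of these fields requires a link to a transfusion.

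**Would mortality reveal TRALI?** Mostly not. With the protocol's case fatality of 5 to 13%, the share surviving is 100 − 13 = 87% to 100 − 5 = 95%.

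**How many cases?** The documents give no incidence for any of the four harms and no expected proportion transfused in either arm. Any case count would rest on assumed rates, so none is given.

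**The case against.** The strongest reply is that this is a pragmatic, open-label trial of two strategies in routine use, and that Section 18.1.2 chooses objective outcomes on purpose to limit bias. Attributing pulmonary oedema or a mild reaction to a transfusion is a judgement made by staff who know the allocation. The randomised comparison of death, kidney injury, infection, ventilation time and ICU stay shows net harm without any such attribution, and transfusion exposure is itself a secondary endpoint. Much of this stands. It is a reason to report these harms descriptively, but not a reason to leave them unrecorded.

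Four stronger readings are tempting and are not supported:

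- A reader might infer that the list in Section 14.12.1 is closed. The text does not say so, and other items such as low output state and surgical complications are collected elsewhere. None of them is one of the four harms.
- A reader might infer that the DSMB receives nothing but these events. Section 17.5 says its safety data include them, and are supplied under a Charter that is not shown.
- A reader might infer that the main risks of the liberal arm are invisible. Severe consequences can appear in the outcomes just listed; what is missing is the named, attributable count.
- A reader might take Section 7.1 as a promise to estimate reaction rates. It describes the consequence for practice of a non-superior result.

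It is also fair to say that the eCRF, the Manual of Operations or the adjudication manual might already contain a reaction field. If so, the protocol should say that it is required.

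**Conclusion.** The point holds in a limited form. The protocol names four harms of its intervention and requires none of them to be recorded as such. A site that follows it exactly supplies no count of transfusion reactions, haemolytic reactions, TRALI or volume-related pulmonary oedema by arm, so neither the DSMB nor the final report can tabulate them from the required data.

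The gap covers all four harms and both arms, since restrictive-arm patients are transfused too. Its size in patients cannot be given from the documents. The validity of the primary comparison is untouched; what is weakened is the safety half of the conclusion. The verdict assumes that the protocol is the binding statement of what sites collect, and that the documents not shown add no such requirement.

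**What to change.** Add four items to the list in Section 14.12.1 and to the eCRF, for both arms: acute transfusion reaction, haemolytic reaction, TRALI, and transfusion-associated overload or pulmonary oedema. Use standard haemovigilance definitions and the chart review that sites already do. State the window as the index hospitalisation: the transfusion records in Section 14.11 run to discharge, whereas Section 14.12.1 stops at day 28. Tabulate the events descriptively by arm in the DSMB safety report and the final report. If the eCRF already holds these fields, a sentence in Section 14.12.1 making them mandatory is enough.

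The cost is a short addition to the eCRF and the time to complete it. No treatment, threshold or primary analysis changes. There are three downsides to state openly. Patients already enrolled need retrospective chart entry or must be reported as not collected. Open-label reporting of softer reactions may differ by arm. The rarer events will be too few for a formal comparison, so the table should carry counts without tests.
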